#### 10.4.8 Assessment of suicidality

Suicidality will be assessed using the Columbia-Suicide Severity Rating Scale (C-SSRS). The scale will be used for Screening as well as to assess suicide ideation and behavior that may occur during the study. All subjects who are  $\geq 6$  years of age will complete the Baseline/Screening version of the C-SSRS at Visit 1 and will complete the Since Last Visit version at subsequent visits. If a subject becomes 6 years of age during the study, the Already Enrolled version of the C-SSRS should be used at the first visit at which the subject is 6 years of age and use the Since Last Visit version at subsequent visits.

The C-SSRS is not validated for subjects  $< 6$  years of age and will not be used for this population. For those subjects, signs and symptoms of depression will be assessed at each visit.

The C-SSRS assessment is completed throughout the study from Visit 1 (entry to study) to Visit 8, and at ETV in case of early termination, and at unscheduled visits. The C-SSRS assessment is also completed during the Transition Period, Taper Period, and at the Safety Follow-Up Visit.

Subject data listings of the data for the C-SSRS will be provided. No summaries of the C-SSRS data are planned.

#### 10.4.9 BRIEF-P and BRIEF assessment

The BRIEF-P/BRIEF assessments are completed at Visit 2 (Baseline), Visit 8, and at ETV in case of early termination.

The BRIEF-P and BRIEF are validated tools that will be used for the evaluation of subjects  $\geq 2$  to  $< 5$  years of age, and  $\geq 5$  years of age, respectively. For each subject, the same version (BRIEF-P or BRIEF) that is used at Visit 2 (Baseline) should be used at Visit 8/ETV.

##### 10.4.9.1 BRIEF-P scores

The BRIEF-P form comprises 63 questions with entry options N (never: scored as 1 point), S (sometimes: scored as 2 points), and O (often: scored as 3 points).

The 63 items are included in the raw Global Executive Composite (GEC) score which ranges from 63 to 189, with higher scores reflecting poorer functioning.

The 3 subscale scores and 5 individual component scores that make up these subscale scores are outlined in [Table 10-5](#).

**Table 10-5: BRIEF-P questionnaire scoring**

Scale/Index	Questions
Inhibit	3, 8, 13, 18, 23, 28, 33, 38, 43, 48, 52, 54, 56, 58, 60, 62
Shift	5, 10, 15, 20, 25, 30, 35, 40, 45, 50
Emotional Control	1, 6, 11, 16, 21, 26, 31, 36, 41, 46
Inhibitory self-control	All from {Inhibit and Emotional Control}
Flexibility	All from {Shift and Emotional Control}

**Table 10–5: BRIEF-P questionnaire scoring**

Scale/Index	Questions
Working Memory	2, 7, 12, 17, 22, 27, 32, 37, 42, 47, 51, 53, 55, 57, 59, 61, 63
Plan/Organize	4, 9, 14, 19, 24, 29, 34, 39, 44, 49
Emergent metacognition	All from {Working Memory and Plan/Organize}
GEC Score	1-63

GEC=Global Executive Composite

Standardized T-scores are determined from each subject’s raw GEC, inhibitory self-control, flexibility, emergent metacognition, and component scores based on the subject’s age and sex. Tables that map each raw score to the appropriate T-score are provided in the BRIEF-P Professional Manual and will be reproduced programmatically.

Calculated T-score values and change from Baseline for the 3 indexed scores and GEC for the BRIEF-P questionnaire will be summarized at Visit 8, and Last Visit, by treatment group.

All BRIEF-P assessment data will be listed.

**10.4.9.2 BRIEF scores**

The BRIEF form comprises 86 questions with entry options N (never: scored as 1 point), S (sometimes: scored as 2 points), and O (often: scored as 3 points).

The first 72 items are included in the GEC score which ranges from 72 to 216, with higher scores reflecting poorer functioning.

The 2 subscale scores and 8 individual component scores that make up these subscale scores are outlined in [Table 10–6](#).

**Table 10–6: BRIEF questionnaire scoring**

Scale/Index	Questions
Inhibit	38, 41, 43, 44, 49, 54, 55, 56, 59, 65
Shift	5, 6, 8, 12, 13, 23, 30, 39
Emotional Control	1, 7, 20, 25, 26, 45, 50, 62, 64, 70
Behavioral Regulation Index (BRI)	All from {Inhibit, Shift, and Emotional Control}
Initiate	3, 10, 16, 47, 48, 61, 66, 71
Working Memory	2, 9, 17, 19, 24, 27, 32, 33, 37, 57
Plan/Organize	11, 15, 18, 22, 35, 36, 40, 46, 51, 53, 58
Organization of Materials	4, 29, 67, 68, 69, 72
Monitor	14, 21, 31, 34, 42, 52, 60, 63

**Table 10–6: BRIEF questionnaire scoring**

Scale/Index	Questions
Metacognition Index (MI)	All from {Initiate, Working Memory, Plan/Organize, Organization of Materials, and Monitor}
GEC Score	1-72

The BRI score is the total of 28 items and ranges from 28-84. The MI score is the total of 44 items and ranges from 44 to 132.

Standardized T-scores are determined from each subject's raw GEC, BRI, MI, and component scores based on the subject's age and sex. Tables that map each raw score to the appropriate T-score are provided in the BRIEF Professional Manual and will be reproduced programmatically.

Calculated T-score values and change from Baseline for the 2 indexed scores (BRI and MI), and GEC for the BRIEF questionnaire will be summarized at Visit 8, and Last Visit, by treatment group.

All BRIEF assessment data will be listed.

This document cannot be used to support any marketing authorization application and any extensions or variations thereof.

REDACTED COPY

---

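### SAP Table 10-6 places BRIEF item 28 in no component scale, so the Metacognition Index as listed has 43 items (43 to 129) against the stated 44 (44 to 132)

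*SAP*

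**What the plan says.** SAP Section 10.4.9.2 scores each BRIEF item 1, 2 or 3. For the Global Executive Composite it says "The first 72 items are included in the GEC score which ranges from 72 to 216". Table 10-6 divides the items into eight component scales and groups these into two indexes. The Behavioral Regulation Index takes Inhibit, Shift and Emotional Control. The Metacognition Index row reads "All from {Initiate, Working Memory, Plan/Organize, Organization of Materials, and Monitor". The GEC row is items 1-72.

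Below the table the SAP gives the size of each index: "The BRI score is the total of 28 items and ranges from 28-84" and "The MI score is the total of 44 items and ranges from 44 to 132".

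Raw scores are converted to T-scores with tables from the BRIEF Professional Manual, which are to be reproduced in the program. T-scores and change from Baseline for BRI, MI and GEC are then summarised at Visit 8 and Last Visit by treatment group.

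**The concern.** The scoring key and the stated totals are both instructions to the programmer, and for MI they disagree. The composition rule takes the items in the five listed rows, and those rows fall one short of the stated count. A program written from the rows would enter a 43-item raw score into a T-score table made for a 44-item scale.

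MI is one of three BRIEF T-scores reported for cognitive function, which the Protocol (Section 4.2.2) and the SAP (Section 2.2.2.2) name as a safety variable. Leaving out an item can only lower the raw score, and the SAP states that higher scores reflect poorer functioning. The error would therefore make the children look better on this measure than their answers show.

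**Working it through.** **Inputs.** Item lists, index composition and stated totals from SAP Section 10.4.9.2 and Table 10-6; each item scores 1 to 3.

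**Formulas.** Index size = sum of items in its component rows. Raw range = 1 × items to 3 × items.

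**Step 1: reproduce the stated BRI.** Inhibit 10 + Shift 8 + Emotional Control 10 = 28 items. Range 28 to 3 × 28 = 84. This matches the SAP.

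**Step 2: do the same for MI.**

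| Component scale | Items listed | Count | Neighbours of 28 in the row |
|---|---|---|---|
| Initiate | "3, 10, 16, 47, 48, 61, 66, 71" | 8 | 16 and 47 |
| Working Memory | "2, 9, 17, 19, 24, 27, 32, 33, 37, 57" | 10 | 27 and 32 |
| Plan/Organize | "11, 15, 18, 22, 35, 36, 40, 46, 51, 53, 58" | 11 | 22 and 35 |
| Organization of Materials | see Table 10-6 | 6 | 4 and 29 |
| Monitor | "14, 21, 31, 34, 42, 52, 60, 63" | 8 | 21 and 31 |

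8 + 10 + 11 + 6 + 8 = 43 items. Range 43 to 3 × 43 = 129. The stated figures are 44 items and 44 to 132, so they are not reproduced.

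**Step 3: find the missing item.** All eight rows together hold 28 + 43 = 71 entries, all distinct and none above 72. Removing them from 1 to 72 leaves one number: 28.

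**Step 4: locate it.** BRI is already at its stated 28 items. GEC is 72 items, and 72 − 28 = 44, the stated size of MI. Protocol Section 11.9.9 describes the scales as nonoverlapping, three in Behavioral Regulation and five in Metacognition. Item 28 therefore belongs in one of the five MI scales. It would fit in numerical order in any of those rows, so the documents do not identify which.

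**Step 5: check the repair.** With item 28 added, MI = 43 + 1 = 44 items, range 44 to 132. BRI + MI = 28 + 44 = 72 items, range 72 to 216, which is the GEC. All stated totals then agree. As printed, BRI + MI covers 71 items, range 71 to 213.

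**Step 6: size of the error if the rows are programmed as printed.** Write x for the item-28 answer.

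- Raw MI as programmed = true MI − x, so it is 1 (never), 2 (sometimes) or 3 (often) points low.
- Error in raw change from Baseline = −(x at the later visit − x at Baseline). Its absolute size is 0 if the answer is unchanged, otherwise 1 or 2.
- A child scored never on every item gets 43, below the stated minimum of 44. A child scored often on every item gets 129 against 132.

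**Control.** The same count on the BRIEF-P key in Table 10-5 finds all 63 of 63 items.

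**Amendments.** Amendment 1, Change #31 removes the validity scales and renames Last Value as Last Visit; it does not alter Table 10-6. Amendment 2 makes no BRIEF change.

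**The case against.** The count itself is hard to dispute. The case on the other side concerns reading and consequence.

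- **Item 28 is not absent from the table.** The GEC row covers 1-72. This stands: the omission is from the eight component scales and hence from MI, and the GEC is unaffected.
- **The SAP carries its own control totals.** With 44 items and 44 to 132 stated, and the manual cited, a careful programmer would notice the gap. This also stands. Whether the program omits item 28 cannot be known from the documents, so the harm is conditional on following the rows as printed.
- **A number can drop out when a table is read from a PDF.** This cannot be excluded entirely. The rows are clean comma-separated sequences with no stray comma or gap, and the neighbouring BRIEF-P key is complete. A look at the source page settles it.
- **Placing item 28 in MI assumes the other items are placed correctly.** The documents confirm the BRI count, not the membership of each item. The inference is strong because adding 28 to MI makes every total agree, but the manual is the authority.
- **The consequence is small.** BRIEF is among the other safety variables, is summarised without a test, and uses one key for both arms and all visits. The MI scale spans 132 − 44 = 88 raw points. All BRIEF data are to be listed, so MI can be recomputed later. These points limit the severity; they do not remove the contradiction.

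**Conclusion.** The concern holds. Table 10-6 as printed gives a 43-item MI (43 to 129), and the text below it states 44 items (44 to 132). Item 28 is the one missing.

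If the rows are programmed as listed, raw MI is 1 to 3 points low at each visit for every respondent who answered item 28. Raw change is off by 0 to 2 points, and one of the five Metacognition component scores is short by the same item. Component T-scores are derived but not summarised. The effect on MI T-scores cannot be worked out here, because the conversion tables are in the manual.

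The reach is limited to subjects aged 5 or over at Visit 2, in countries with a translated BRIEF. BRI, GEC, the BRIEF-P used at age 4, and all efficacy analyses are untouched. No between-arm bias is claimed. If the program already follows the manual's key, the correction is to the document only. It should be made in either case, because the reported safety score depends on which instruction is followed.

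**What to change.** Look up item 28 in the BRIEF Professional Manual, which the SAP already cites, and add it to the correct Metacognition row of Table 10-6. In the scoring program, confirm that MI uses 44 items, that raw MI lies between 44 and 132, and that BRI + MI = GEC for every complete record.

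The cost is one number in a table, one line of code and one program check. The sponsor has made a correction of this kind before: Amendment 2, Change #17 replaced a single wrong item number (28 for 82) in the CBCL/1½-5 key.

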## 12 APPENDICES

### 12.1 Marked abnormality criteria for laboratory data

#### 12.1.1 Marked abnormality criteria for hematology data

**Table 12–1: Hematology abnormality criteria**

Parameter	Age Range	Unit (conventional)	Abnormality criteria (conventional unit)	Unit (standard)	Abnormality criteria (standard unit)
Hematocrit	<2y	%	≤27 >45	%	≤27 >45
	2y - <17y	%	≤29 >47	%	≤29 >47
	≥17y	%	≤85% of LLN ≥115% of ULN	%	≤85% of LLN ≥115% of ULN
Hemoglobin	<2y	g/dL	≤9.0 >15.0	g/L	≤90 >150
	2y - <17y	g/dL	≤9.5 >16.0	g/L	≤95 >160
	≥17y	g/dL	≤85% of LLN ≥115% of ULN	g/L	≤85% of LLN ≥115% of ULN
WBC/ Leukocytes	All	10  /L	≤3.0 ≥16.0	G/L	≤3.0 ≥16.0
Lymphocytes Absolute	<2y	10  /L	<1.0 >9.8	G/L	<1.0 >9.8
	2y - <6y	10  /L	<0.7 >6.9	G/L	<0.7 >6.9
	≥6y	10  /L	<0.6 >5.0	G/L	<0.6 >5.0
Basophils	>1m	%	≥5.0	%	≥5.0
Basophils Absolute	>1m	10  /L	≥0.4	G/L	≥0.4
Eosinophils	>1m	%	≥10	%	≥10
Eosinophils Absolute	>1m	10  /L	≥1.0	G/L	≥1.0
Monocytes	>1m	%	≥20.0	%	≥20.0

**Table 12–1: Hematology abnormality criteria**

Parameter	Age Range	Unit (conventional)	Abnormality criteria (conventional unit)	Unit (standard)	Abnormality criteria (standard unit)
Monocytes Absolute	>1m	10  /L	≥2.0	G/L	≥2.0
Neutrophils Absolute	>1m	10  /L	<1.5	G/L	<1.5
Platelets	>1m	10  /L	≤100 ≥600	G/L	≤100 ≥600
RBC/ Erythrocytes	<2y	10  /L	<3.0	T/L	<3.0
	≥2y	10  /L	<3.5	T/L	<3.5

Abbreviations: m =month, y = year. A month is defined as 30 days; a year is defined as 365.25 days.

**12.1.2 Marked abnormality criteria for chemistry data**

**Table 12–2: Chemistry abnormality criteria**

Parameter	Age Range	Unit (conventional)	Abnormality criteria (conventional unit)	Unit (standard)	Abnormality criteria (standard unit)
AST (SGOT)	All	U/L	≥3.0 x ULN ≥5.0 x ULN ≥10.0 x ULN	U/L	≥3.0 x ULN ≥5.0 x ULN ≥10.0 x ULN
ALT (SGPT)	All	U/L	≥3.0 x ULN ≥5.0 x ULN ≥10.0 x ULN	U/L	≥3.0 x ULN ≥5.0 x ULN ≥10.0 x ULN
Alkaline Phosphatase	<4y	U/L	≥690	U/L	≥690
	4y - <10y	U/L	≥834	U/L	≥834
	10y - <17y	U/L	≥1761	U/L	≥1761
	≥17y	U/L	≥3.0 x ULN	U/L	≥3.0 x ULN
GGT	<6m	U/L	≥522	U/L	≥522
	6m - <1y	U/L	≥279	U/L	≥279
	1y - <13y	U/L	≥66	U/L	≥66
	13y - <17y	U/L	≥126	U/L	≥126
	≥17y	U/L	≥3.0 x ULN	U/L	≥3.0 x ULN

**Table 12–2: Chemistry abnormality criteria**

Parameter	Age Range	Unit (conventional)	Abnormality criteria (conventional unit)	Unit (standard)	Abnormality criteria (standard unit)
Total Bilirubin	>1m	mg/dL	≥2.0	umol/L	≥34.208
Total Protein	2m-<1y	g/dL	<3.0 >11.9	g/L	<30 >119
	1y - <17y	g/dL	<4.3 >12.0	g/L	<43 >120
	≥17y	g/dL	<4.3 >13.0	g/L	<43 >130
Albumin	<1y	g/dL	<1.6 >7.2	g/L	<16 >72
	≥1y - <17y	g/dL	<2.4 >8.4	g/L	<24 >84
	≥17y	g/dL	<2.6 >8.4	g/L	<26 >84
BUN	<1y	mg/dL	≥24	mmol/L	≥8.568
	1y - <17y	mg/dL	≥36	mmol/L	≥12.852
	≥17y	mg/dL	≥40	mmol/L	≥14.28
Urea	<1y	mg/dL	>42	mmol/L	>7.014
	≥1y	mg/dL	>60	mmol/L	>10.02
Creatinine	1y - <10y	mg/dL	>1.2	umol/L	>106.8
	10y - <16y	mg/dL	>1.8	umol/L	>159.12
	≥16y	mg/dL	≥2.0	umol/L	≥176.8
Creatinine Clearance a b	All	mL/min	<50	mL/s	<0.835
Bicarbonate	>1m - <17y	mEq/L	<15 >38	mmol/L	<15 >38
	≥17y	mEq/L	<18 >38	mmol/L	<18 >38
Calcium	<1y	mg/dL	<6.9 >12.2	mmol/L	<1.725 >3.05
	1y - <17y	mg/dL	<7.4 >11.7	mmol/L	<1.85 >2.925

**Table 12–2: Chemistry abnormality criteria**

Parameter	Age Range	Unit (conventional)	Abnormality criteria (conventional unit)	Unit (standard)	Abnormality criteria (standard unit)
	≥17y	mg/dL	≤7.6 ≥11.0	mmol/L	≤1.9 ≥2.75
Chloride	>1m	mEq/L	≤90 ≥112	mmol/L	≤90 ≥112
Phosphorous	<1y	mg/dL	<1.8 >8.2	mmol/L	<0.5814 >2.6486
	1y - <17y	mg/dL	<1.8 >7.4	mmol/L	<0.5814 >2.3902
	≥17y	mg/dL	≤2.0 ≥6.0	mmol/L	≤0.646 ≥1.938
Potassium	<1y	mEq/L	≤3.0 ≥6.5	mmol/L	≤3.0 ≥6.5
	≥1y	mEq/L	≤3.0 ≥6.0	mmol/L	≤3.0 ≥6.0
Sodium	>1m	mEq/L	<127 >151	mmol/L	<127 >151
Glucose	>1m - <17y	mg/dL	<50 ≥180	mmol/L	<2.775 ≥9.99
	≥17y	mg/dL	<50 ≥200	mmol/L	<2.775 ≥11.1
Total Cholesterol	≥1y	mg/dL	>250	mmol/L	>6.475
LDL (calculated)	1y - <17y	mg/dL	>140	mmol/L	>3.626
	≥17y	mg/dL	>200	mmol/L	>5.18
HDL	≤2y	mg/dL	<10	mmol/L	<0.259
	>2y	mg/dL	<20	mmol/L	<0.518
Triglycerides	<1y	mg/dL	>750	mmol/L	>8.475
	≥1y	mg/dL	>300	mmol/L	>3.39
Uric Acid	<1y	mg/dL	>7.7	umol/L	>457.996
	1y - <13y	mg/dL	>6.5	umol/L	>386.62

**Table 12–2: Chemistry abnormality criteria**

Parameter	Age Range	Unit (conventional)	Abnormality criteria (conventional unit)	Unit (standard)	Abnormality criteria (standard unit)
	13y - <17y	mg/dL	>8.6	umol/L	>511.528
	≥17y	mg/dL	>9.5	umol/L	>565.06
Thyroxine (T4)	<1y	ug/dL	≤4.3 ≥18.4	nmol/L	≤55.3453 ≥236.8264
	≥1y	ug/dL	≤3.8 ≥13.5	nmol/L	≤48.9098 ≥173.7585
Globulin	<1y	g/dL	<1.0 >4.5	g/L	<10 >45
	≥1y	g/dL	<1.2 >5.3	g/L	<12 >53

Abbreviations: ALT= alanine aminotransferase; AST = aspartate aminotransferase; BUN = blood urea nitrogen; dL = deciliter; GGT: gamma-glutamyltransferase; HDL = high density lipoprotein; LDL = low density lipoprotein; L = liter; m = month (a month is defined as 30 days) mg = milligram; mmol = millimoles; µg = microgram; U = unit; ULN = upper limit of normal; y = years (a year is defined as 365.25 days)

a Schwartz equation (patients <12): Cr Cl ml/min = [Height (cm) \* 0.55] / serum creatinine

b Cockcroft equation (patients >12): Male: Cr Cl ml/min = [(140-age) x body weight (kg)] / (72 x serum creatinine); Female: Cr Cl ml/min = [(140-age) x body weight (kg)] / (72 x serum creatinine) x 0.85

## 12.2 Other significant adverse events

MedDRA Preferred Term
HEPATOTOXICITY RELATED TERMS
Hepatitis toxic
Hepatotoxicity
CARDIAC AND ECG RELATED TERMS
Atrioventricular block third degree
Atrioventricular block second degree
Bradycardia
Bradycardia
Cardiac pacemaker insertion
Atrial fibrillation
Atrial flutter
Sinus bradycardia
Ventricular tachycardia
Ventricular fibrillation
Heart Rate decreased
Sick sinus syndrome
SUICIDALITY RELATED TERMS
Completed suicide
Depression suicidal
Suicidal behavior
Suicidal ideation
Suicide attempt
Intentional self-injury
Self injurious behavior
Self-injurious ideation
Intentional overdose
Multiple drug overdose intentional
Poisoning deliberate
ADDITIONAL TERMS
Loss of consciousness
Syncope

This document cannot be used to support any marketing authorization application and any extensions or variations thereof.

## **13 AMENDMENTS TO THE STATISTICAL ANALYSIS PLAN**

### **13.1 Amendment 1**

The primary purpose of this substantial amendment is for consistency with other SAPs and protocols in the LCM pediatric program.

#### **Global change**

The following global change was made throughout the SAP:

- Last Value has been changed to Last Visit
- WHO-DD has been changed to WHODD
- For AEs, primary SOC is now written as MedDRA primary SOC
- References to Appendix 12 (Table 12.2) have been changed to reference Appendix 12 (section 12.2)

#### **Specific changes**

##### **Change #1**

Added ANCOVA – analysis of covariance to the list of abbreviations

Added MA – markedly abnormal to the list of abbreviations.

##### **Change #2**

The statistical analysis plan signature page has been removed and the new e-signature page has been included in its place.

##### **Change #3**

#### **Section 2.2.1.3 Other efficacy variables**

Other efficacy variables to be examined include:

- Clinical Global Impression of Change at the end of the Maintenance Period
- Caregiver's Global Impression of Change at the end of the Maintenance Period
- Quality of life assessments (PedsQL)
- Health care resource use (concomitant AEDs, medical procedures, health care provider consultations not related to study, hospitalizations not related to study)

#### **Has been changed to:**

Other efficacy variables to be examined include:

- Clinical Global Impression of Change at the end of the Maintenance Period
- Caregiver's Global Impression of Change at the end of the Maintenance Period
- Quality of life assessments (PedsQL)
- Health care resource use (concomitant AEDs, medical procedures, health care provider consultations including hospitalizations not foreseen by the protocol)

## Change #4

### Section 2.3 Study design and conduct

Subjects who complete the Maintenance Period and plan to participate in the open-label extension study (EP0034) will enter a 4-week blinded Transition Period. Subjects randomized to LCM will maintain their Maintenance Period dose during the Transition Period. Subjects randomized to placebo will transition to LCM in a double-blind fashion in accordance with the schedule provided in Table 3-4.

The blinded Taper Period (2 to 4 weeks, depending on dose level achieved) is for subjects who will not be entering the open-label extension study (EP0034) for any of the following reasons:

- Subject does not complete the Titration Period, the Maintenance Period, or the Transition Period
- Subject does not choose to enroll in the open-label extension study (EP0034) after completing the Maintenance Period or the Transition Period

Taper of LCM may not be required for some subjects who discontinue study medication prematurely, depending on the treatment option selected by the investigator in consultation with the subject and/or parent/legal representative.

The dosing of study medication for the Taper Period is provided in Table 3-5.

There will be a 30-day Safety Follow-Up Period for subjects not entering the open-label extension study (EP0034).

Unscheduled visits can be conducted at the discretion of the investigator.

Each subject's total duration of study medication administration is up to 24 weeks. The total study duration can be up to 36 weeks, including the 30-day safety Follow-Up Period.

Detailed tabular schedules of study procedures are provided in Table 2-1, Table 2-2, and Table 2-3.

**Table 2-1: Schedule of study assessments (Baseline Period, Titration Period, Maintenance Period, Early Termination Visit, and Unscheduled Visits)**

Assessments	Baseline Period (8 weeks)			Treatment Period (16 weeks)										ETV	Unscheduled Visit c	
				Titration Period (6 weeks)						Maintenance Period (10 weeks)						
Visit	V1 a	T1	V2	T2	V3	T3	V4	T4	V5	V6	T5	V7	T6	V8 b		
Week in study	-8	-4	0	1	2	3	4	5	6	8	10	12	14	16		
Informed consent	X															
Inclusion/exclusion criteria	X	X	X													
Medical history	X															
Seizure history	X															
Concomitant medications	X	X	X	X	X	X	X	X	X	X	X	X	X	X	X	X
Concomitant AEDs	X	X	X	X	X	X	X	X	X	X	X	X	X	X	X	X
VNS assessment d	X		X		X		X		X	X		X		X	X	X
Physical examination (complete)	X		X											X	X	
Physical examination (brief)					X		X		X	X		X				
Tanner Stage e	X													X	X	
Vital signs (BP and pulse rate, including orthostatic assessments)	X		X		X		X		X	X		X		X	X	X
Body weight	X		X		X		X		X	X		X		X	X	X
Height	X		X											X	X	
Head circumference	X													X	X	
Neurological examination (complete)	X		X											X	X	

**Table 2-1: Schedule of study assessments (Baseline Period, Titration Period, Maintenance Period, Early Termination Visit, and Unscheduled Visits)**

Assessments	Baseline Period (8 weeks)			Treatment Period (16 weeks)											ETV	Unscheduled Visit c
	Visit	Titration Period (6 weeks)						Maintenance Period (10 weeks)								
Week in study	V1 a	T1	V2	T2	V3	T3	V4	T4	V5	V6	T5	V7	T6	V8 b		
Neurological examination (brief)					X		X		X	X		X				
ECG (12-lead) f	X		X		X		X		X	X		X		X	X	
Clinical chemistry/hematology	X		X				X		X			X		X	X	
Endocrinology			X											X	X	
Urinalysis g	X		X				X		X			X		X	X	
Serum pregnancy test h	X						X		X			X		X	X	
Urine pregnancy test h			X		X					X						
Concomitant AED plasma concentrations i	X								X					X	X	
LCM plasma concentration i	X								X					X	X	
C-SSRS j	X		X		X		X		X	X		X		X	X	X
Clinical Global Impression of Change														X	X	
Caregiver's Global Impression of Change														X	X	
Achenbach CBCL k			X						X					X	X	
BRIEF-P/BRIEF l			X											X	X	
PedsQL m			X											X	X	
Contact IXRS	X		X		X		X		X	X		X		X	X	

**Table 2-1: Schedule of study assessments (Baseline Period, Titration Period, Maintenance Period, Early Termination Visit, and Unscheduled Visits)**

Assessments	Baseline Period (8 weeks)			Treatment Period (16 weeks)											ETV	Unscheduled Visit c
	Visit	Titration Period (6 weeks)						Maintenance Period (10 weeks)								
Visit	V1 a	T1	V2	T2	V3	T3	V4	T4	V5	V6	T5	V7	T6	V8 b		
Week in study	-8	-4	0	1	2	3	4	5	6	8	10	12	14	16		
Randomization n			X													
Dispense study medication			X l		X		X		X	X		X		X	X	
Study medication return					X		X		X	X		X		X	X	
Subject diary o	X	X	X	X	X	X	X	X	X	X	X	X	X	X	X	X
Withdrawal criteria		X	X	X	X	X	X	X	X	X	X	X	X	X		X
AE reporting	X	X	X	X	X	X	X	X	X	X	X	X	X	X	X	X
Assessments of epilepsy surgery/VNS	X															
Health care resource use	X		X		X		X		X	X		X		X	X	

AE=adverse event; AED=antiepileptic drug; BP=blood pressure; BRIEF=Behavior Rating Inventory of Executive Function; BRIEF-P=Behavior Rating Inventory of Executive Function-Preschool Version; CBCL=Child Behavior Checklist; C-SSRS=Columbia-Suicide Severity Rating Scale; ECG=electrocardiogram; ETV=Early Termination Visit; IXRS=interactive voice/web response system; LCM=lacosamide; PedsQL=Pediatric Quality of Life Inventory; T=Telephone Contact; V=Visit; VNS=vagus nerve stimulation

Note: For all visits shown in Table 2-1 a time window of ±2 days relative to Visit 2 (Baseline Period) is applicable. During the Treatment Period, each visit should occur at the end of the week indicated in accordance with this time window.

aVisit 1 (V1) may occur over more than 1 day; however, all results of Visit 1 assessments should be available before T1.

bAt the end of Visit 8, subjects who complete the Maintenance Period may be eligible to participate in an open-label extension study (EP0034). Subjects who plan to enroll in the open-label extension study will proceed to a 4-week blinded Transition Period. Subjects who choose not to enter the open-label extension study or who do not complete the Maintenance Period will proceed to a blinded Taper Period (2 to 4 weeks, depending on dose level achieved). Taper of LCM may not be required for some subjects who discontinue study medication prematurely, depending on the treatment option selected by the investigator in consultation with the subject and/or parent/legal representative.

cIf an Unscheduled Visit is needed (eg, due to AE), then the assessments noted will be performed. Additional assessments may be performed at the investigator's discretion. The C-SSRS will be completed at an Unscheduled Visit only if the visit is related to an AE.

dOnly applicable for subjects with an implanted VNS device.

eThe Tanner Stage will be performed only for subjects who are pubescent at Visit 1 or who enter puberty during the course of the study.

fA 12-lead ECG (2 interpretable recordings) will be performed prior to any blood draws and vital signs assessment. The subject should rest in the supine position for approximately 5 minutes before the recordings and during the recordings, if possible. The recordings should be made 20 to 30 minutes apart.

gUrinalysis will be performed for subjects  $\geq 5$  years of age only.

hPregnancy tests will be performed for female subjects of childbearing potential only.

iBlood samples for analysis of concomitant AED plasma concentrations and/or LCM will be drawn along with clinical chemistry, hematology, and endocrinology samples, as applicable.

jThe C-SSRS will be completed for all subjects  $\geq 6$  years of age. The C-SSRS will be completed at an Unscheduled Visit only if the visit related to an AE.

kThe Achenbach CBCL: CBCL/1½ -5 for children 18 months to 5 years and 11 months of age, and CBCL/6-18 for children  $\geq 6$  years to  $< 17$  years of age; to be completed by the parent(s)/legal representative(s) (estimated completion time 45 minutes). For each subject, the same version of the scale that was completed at Visit 2 (CBCL/1½ -5 or CBCL/6-18) should be maintained for the duration of the study and should be completed by the same parent/legal representative. The Achenbach CBCL will be used only in countries where a translated version is available.

lThe BRIEF-P should be used for subjects who are  $\geq 2$  years to  $< 5$  years of age at Visit 2, and the BRIEF should be used for subjects who are  $\geq 5$  years of age at Visit 2. The same version of the scale that was completed at Visit 2 (BRIEF-P or BRIEF) should be maintained for each subject for the duration of the study. The BRIEF-P and BRIEF will be used only in countries where a translated version is available.

mThe version of the PedsQL used at Visit 2 should be consistent with the subject's age at Visit 2 and should be maintained for each subject for the duration of the study. The PedsQL will be used only in countries where a translated version is available.

nAt the end of Visit 2, subjects should take the first dose of study medication in the clinic.

oThe subject diary will be dispensed at Visit 1. At all subsequent visits, the subject and/or legal representative(s) will be reminded to complete the diary on a daily basis.

